## Sex Effects on Blood Pressure With Handgrip Training

### Research protocol

This study will be designed as a randomized, controlled, cross-over, repeated measures experiment. Fifty young healthy adult participants (25 males and 25 females) will visit the laboratory three times to perform a fatiguing bout of isometric handgrip exercise before and after both 4 weeks of isometric handgrip training and a no-exercise training condition. Participants will be randomly allocated to the isometric handgrip and the non-exercise training conditions using an online program (<http://www.randomizer.org/>). Participants that start with isometric handgrip training will return to the laboratory after a 4-wk washout, as this duration has been shown to decondition cardiovascular outcomes following training (1–3). To eliminate diurnal variation, each participant will visit the laboratory at the same time of day. Main outcomes in each visit will be measured at rest, during the fatiguing bout of isometric handgrip exercise, and 5, 10, 30, and 60-min post-exercise (see figure and Table 1). These measurement timings are aimed to characterize BP, and the cardiac autonomic and vascular function biphasic responses (4–6). Visits 2 and 3 will take place within 7 days of the last training session.

**Figure 1:** Experimental design, a randomized, controlled, cross-over, repeated measurements study. Abbreviations: CON; control, BRS baroreflex sensitivity, RMSSD, root mean square of

**Table 1** Procedures to be conducted in each visit to the laboratory

Procedures	Time (min)
Rest	15
Measurements	
1) BP, arterial stiffness, cardiac autonomic function	5
2) Brachial endothelial function (FMD)	15
Fatiguing isometric handgrip exercise	~ 3-5
Last isometric contraction	
Measurements	
1) BP, brachial blood flow	
2) Cardiac autonomic function (BRS, RMSSD, HF)	
Post 5 min	
Measurements	
1) BP, arterial stiffness (cfPWV), cardiac autonomic function (BRS, RMSSD, HF)	5
Post 10 min	
Measurements	
1) Brachial endothelial function (FMD)	15
Post 30 min	
Measurements	
1) BP, arterial stiffness (cfPWV), cardiac autonomic function (BRS, RMSSD, HF)	5
2) Brachial endothelial function (FMD)	15
Post 60 min	
Measurements	
1) BP, arterial stiffness (cfPWV), cardiac autonomic function	5
2) Brachial endothelial function (FMD)	15
	Total ~ 100

successive differences; HF, high-frequency power band; FMD; brachial artery flow-mediated dilation, cfPWV; central pulse wave velocity.

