### Individual blood pressure responsiveness to isometric handgrip training

We aim to conduct an exploratory analysis of the individual BP responsiveness to isometric handgrip training. Participants will be classified as showing relevant (responder) or negligible (non-responder) training-related hypotensive effects using the ROPE + HDI decision rule to reject or non-reject the null – a Bayesian method (38,39). Briefly, this method estimates the percentage of the highest density interval (HDI, like CI in frequentist statistics) within the range of values around the null – region of practical equivalence (ROPE). This estimated percentage corresponds to different levels of significance that will guide the training-related hypotension individual response classification with non-responders defined as > 99 %, likely responders < 5%, and responders < 1% of HDI within the ROPE (38,39).

The HDI calculated as an 89% credible interval will be derived from each participant's posterior normal distribution obtained from 1000 simulations based on the individual pre-to-post change in SBP and DBP (delta) and respective standard deviations calculated as TE/2, where TE is the technical error calculated as CV/2 \*100) (38–40). Individual normal distributions will be derived using the R's rnorm function. We will estimate the ROPE as 20% of the baseline SBP and DBP standard deviations in each group (sex) and this represents the smallest worthwhile difference (41–43). Both the HDI and the ROPE will be computed with R package bayestestR (44). Participants will then be classified according to the ROPE + HDI decision rule. This method of classifying responders mitigates some pitfalls of the traditional response threshold binary classification, such as not accounting for within-participant measurement error variability associated with blood pressure or the magnitude of group differences in mean response (40,41,45).

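### The responder rule calls a pre-to-post BP change training-related without referring it to the participant's own no-exercise condition, so a downward drift between visits raises the chance of a responder label

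*Combined protocol and SAP*

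**What the plan says.** The Research protocol section gives every participant both conditions, with measurements "before and after both 4 weeks of isometric handgrip training and a no-exercise training condition", over three laboratory visits.

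The responder analysis is introduced as exploratory: "We aim to conduct an exploratory analysis of the individual BP responsiveness to isometric handgrip training". Its label carries a causal meaning: "Participants will be classified as showing relevant (responder) or negligible (non-responder) training-related hypotensive effects". The ingredients are:

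- the quantity classified: a posterior simulated "based on the individual pre-to-post change in SBP and DBP (delta");
- its spread: "respective standard deviations calculated as TE/2, where TE is the technical error calculated as CV/2", multiplied by 100;
- the interval: "The HDI calculated as an 89% credible interval";
- the comparison zone, "within the range of values around the null": "We will estimate the ROPE as 20% of the baseline SBP and DBP standard deviations in each group (sex");
- the cut-offs: under 5% of the HDI inside the ROPE for a likely responder, under 1% for a responder, over 99% for a non-responder.

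Training condition appears as a fixed effect in the linear mixed model under Statistical analysis. It does not appear in the responder rule.

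**The concern.** The question asked is whether training lowered this person's BP by more than a negligible amount. The rule answers a different one: whether this person's BP fell by more than a negligible amount between two visits. The answers differ whenever BP moves for another reason, such as growing used to the laboratory, or season.

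The rule sees only the change. A fall of X mmHg from drift with no training effect, and a fall of X mmHg from training with no drift, give the same distribution of labels. Correcting the posterior SD or adding a direction condition leaves this as it is. The share of responders could then be reported as individual training effects when part of it is not. The section's closing sentence says the method helps with the magnitude of group differences in mean response, but no listed step uses the control mean or the control change.

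The word *pre* adds to the problem. With three visits it could be visit 1 for everyone, or the visit just before training, which in control-first participants is visit 2. The section does not say.

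**Working it through.** **No figure to reproduce.** The plan states no error rate for the responder rule. Its one computed figure, the total of 50 participants, concerns the mixed ANOVA and plays no part here.

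**Inputs from the plan.** 89% HDI; ROPE half-width 0.2 × baseline SD; under 5% cut-off (responder or likely responder); posterior SD of TE/2.

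**Assumed inputs, because the documents give none.** Within-person visit error SD s = 5 mmHg (range 4–6); baseline SBP SD 10 mmHg (range 8–10), so ROPE = ±2 mmHg; TE read as s in mmHg, so TE/2 = 2.5 mmHg. There is no training effect. Only falls are counted, although the rule as written has no direction condition.

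**Step 1: how far must BP fall to be labelled?** For a normal posterior the 89% HDI is delta ± 1.598 × SD. Less than 5% of its mass lies in the ROPE when Φ((−2 − delta)/SD) exceeds 0.945 − 0.05 × 0.89 = 0.9005, that is z = 1.284. The cut-off is therefore delta < −2 − 1.284 × SD.

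- SD for a two-visit difference, √2 × 5 = 7.07: −2 − 9.08 = −11.08 mmHg.
- SD of TE/2 = 2.5: −2 − 3.21 = −5.21 mmHg.

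**Step 2: how often is it crossed with no training effect?** The observed change is N(drift, 7.07), so the rate is Φ((cut-off − drift)/7.07).

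| Drift (mmHg) | SD = √2 × s | SD = TE/2 |
|---|---|---|
| +2 | Φ(−1.85) = 3% | Φ(−1.02) = 15% |
| 0 | Φ(−1.57) = 6% | Φ(−0.74) = 23% |
| −2 | Φ(−1.28) = 10% | Φ(−0.45) = 32% |
| −4 | Φ(−1.00) = 16% | Φ(−0.17) = 43% |
| −5 | Φ(−0.86) = 19% | Φ(−0.03) = 49% |

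Over the assumed ranges, the √2 × s column is 5–7% at no drift, 10–11% at −2, 15–19% at −4 and 18–25% at −5. Much of the TE/2 column comes from that SD being too small for a change score: 23% are labelled with no drift at all.

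**Step 3: does a control-referenced contrast remove the dependence?** Let d be post-training minus post-control BP: visit 2 minus visit 3 in training-first participants, visit 3 minus visit 2 in control-first participants. A visit 2-to-3 shift P enters d as −P and +P. Half the difference between the sequence means of d (control-first minus training-first) estimates P, which is then added back in training-first and subtracted in control-first participants. In a simulated 50-person trial with s = 5, posterior SD 7.07 and no training effect, the labelled share stays at 5.7% for every drift pattern tried.

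**Step 4: leftover training effect.** If an effect L remains at visit 3 in training-first participants, their mean d is T − L − P, and in control-first participants it is T + P. The estimated shift is P + L/2, so the adjusted contrast is T − L/2 in both sequences. For T = −5 and L = −3 this gives −3.5.

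**The case against.** Several points on the other side stand.

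- A reader might infer that any drift is labelled a response, or that the rule tests against exactly zero. Neither is so. The comparison is with a ROPE, and a small drift only raises the probability of a label: a 2 mmHg fall moves it from 6% to 10%, about 2 people in 50.
- A reader might infer that the control visit is never used. The text does not settle this. If *pre* means the visit before training, control-first participants are already compared with their post-control visit. Drift during the training period itself would still remain, and training-first participants would still have no control reference.
- The BP ceiling for entry does not support a worry about false responders through regression to the mean. Selecting low readings tends to push later readings up, which lowers the rate.
- Nothing in the documents supports a drift of 4–5 mmHg. The 5 mmHg under Sample size is a detectable mean difference taken from a study of acute exercise. The plan also fixes time of day, rest, room temperature, fasting and caffeine, and averages the last two of three cuff readings. These steps make large drift less likely but do not replace a control.
- The section uses sex to set the ROPE and states no comparison of responder shares by sex, so no bias in such a comparison can be charged to the plan.

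The strongest objection is that the analysis is exploratory and the training-versus-control comparison is made in the mixed model. That limits the severity. It does not answer the point that a label called training-related is derived without the control condition.

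**Conclusion.** The point holds in a limited form. As described, the responder rule attributes a raw pre-to-post change to training, has no control reference and leaves *pre* undefined. Downward drift raises the chance of a responder label and the rule cannot tell it from a training effect; upward drift lowers that chance.

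Under the assumed SDs, a 4–5 mmHg fall raises the labelled share from about 6% to 16–19% with a correct two-visit SD, and from 23% to 43–49% with TE/2 read as mmHg. These are illustrations: baseline SD, technical error and drift are all assumed. The defect is confined to the exploratory responder labels; a reader should not carry it over to the linear mixed model. It should be corrected before responder shares are reported as training effects.

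**What to change.** In the section on individual blood pressure responsiveness:

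1. Define the classified quantity as each participant's post-training minus post-control resting BP, stating by sequence which of visits 2 and 3 closes each condition, after removing the estimated visit 2-to-3 period shift.
2. Set the posterior SD to the error of that difference, √2 × the within-person visit error in mmHg, in place of TE/2. Changing the contrast without changing the SD would leave the high rate at zero drift.
3. If the pre-to-post change is kept, define *pre* by sequence, describe the labels as observed change and not as training-related, and report the same classification for the control-condition change beside it.

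The cost is SAP wording and a few lines of R. Both visits are already planned, and a difference of two visits carries the same noise as pre-to-post. There are two downsides: participants missing visit 2 or 3 are not classified, and any training effect L left after washout shrinks the contrast by L/2 in both sequences.

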#### *Blood pressure*

Participants will be asked to wear a non-invasive inflating and deflating finger cuff during all study visits. This will allow beat-to-beat BP to be recorded using finger plethysmography (Finometer; Finapres Medical System, Amsterdam, The Netherlands) before, during, and after isometric handgrip exercise in the supine position. Beat-to-beat BP will be averaged offline over 2 to 5-min using Lab Chart 8 (ADIInstruments, BellaVista, NSW, Australia). Beat-to-beat dynamic fluctuations in BP induced by acute isometric handgrip exercise will be quantified through BP variability indices including spectral methods using the adapted HRV module of Lab Chart 8. This will give insight into sympathetic outflow to blood vessels (14,15).

**Brachial BP** of the right arm will also be measured three times at 1-minute intervals before and after isometric handgrip exercise using an automated blood pressure cuff (HEM-7311-ZSA; Omron Healthcare Co, Ltd, Kyoto, Japan) (16). Measurements will be accepted if they do not differ > 4 mmHg, and the average of the last two will be used for data analysis (16). Mean arterial pressure will be estimated as  $2/3 \text{ DBP} + 1/3 \text{ SBP}$ .

**Central BP** will be assessed via carotid artery tonometry (NIHem, Cardiovascular Engineering Inc., Norwood, MA). Brachial systolic and diastolic cuff BPs will be used to calibrate the peak and trough of the signal-averaged pressure waveforms. Carotid pressure waveforms will be calibrated with diastolic and integrated mean brachial cuff pressure. Central BP is then estimated from the calibrated carotid pressure. Central pulse pressure will be calculated as the difference between the peak and trough of the calibrated carotid pressure waveform.

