### Sample size

Based upon an effect size of 0.160 and a drop-out rate of 15%, a priori power analysis (G-Power Version 3.1.9.3) for mixed ANOVA suggested a total of 50 participants are required to detect SBP mean differences of at least 5 mmHg over time and groups ( $\alpha = 0.05$ ,  $1-\beta=0.80$ ). Despite this mean difference obtained from a study that characterized BP responses after acute isometric handgrip exercise (7), we also aim to examine the effects of training on acute blood pressure responses to isometric handgrip exercise. Thus, given these differences in study design, we additionally set the effect size considering the small, standardized effect sizes ( $\leq 0.20$ ) for exercise training sciences (31).

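### Exploratory responder rule: the SD given to each pre-to-post BP change has no route to mmHg, is too small for a two-visit difference if TE is a visit-value error, and the cut-offs leave 5-99% without a class

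*Combined protocol and SAP*

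**What the plan says.** The section on individual blood pressure responsiveness to isometric handgrip training describes an exploratory Bayesian rule. Each participant gets a normal distribution of 1000 simulated values, built from the "individual pre-to-post change in SBP and DBP (delta") and "respective standard deviations calculated as TE/2, where TE is the technical error calculated as CV/2". The printed formula continues with a multiplication by 100 and a closing bracket that has no partner.

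The 89% highest density interval (HDI) of that distribution is compared with a ROPE of 20% of the baseline SBP or DBP standard deviation in each sex. Participants with more than 99% of the HDI inside the ROPE are non-responders; the other classes are "likely responders < 5%, and responders < 1% of HDI within the ROPE". The purpose is a "training-related hypotension individual response classification". The section prefers this rule to a simple threshold because the latter has the pitfall of "not accounting for within-participant measurement error variability associated with blood pressure".

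The section names no BP method. For the brachial cuff, the Blood pressure section says: "Measurements will be accepted if they do not differ > 4 mmHg, and the average of the last two will be used".

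**The concern.** The rule depends on one input, the SD attached to each person's change. Three things about it, and about the classes built on it, look wrong.

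- **Units.** The change and the ROPE are in mmHg. TE is built from a CV, which is relative, and nothing multiplies it by a BP level. The documents give no CV for BP.
- **Size.** A change is a difference between two visits and carries the error of both. Halving a technical error moves the SD the wrong way if that error belongs to one visit value.
- **Classes.** Nothing is stated for 5-99% of the HDI inside the ROPE, although the stated aim is to classify participants.

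An SD that is too small gives an interval that is too narrow, so measurement noise is reported as individual training response. That would defeat the reason given for choosing the method.

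**Working it through.** The plan states no numerical result for this rule, so there is no figure to reproduce.

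**Inputs from the plan:** SD = TE/2; 89% HDI, half-width 1.598 x SD for a normal distribution; ROPE = 0.20 x baseline SD; cut-offs 1%, 5% and 99%; visit value = mean of the last two cuff readings; 5 mmHg as the SBP difference of interest in the Sample size section.

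**Assumptions, not in the documents:** mean SBP 115 mmHg; baseline SD 10 mmHg, so ROPE = +/-2 mmHg; visit-value CV 2-5%, so TE = 0.02 x 115 = 2.30 to 0.05 x 115 = 5.75 mmHg.

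**Step 1, size of the SD.** With visit-value error TE and independent visits, SD(change) = sqrt(TE^2 + TE^2) = sqrt(2) x TE. The ratio to TE/2 is 2 x sqrt(2) = 2.83. If a root sign was lost and TE/sqrt(2) was meant, the ratio is 2.

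**Step 2, coverage.** The interval covers the true change with probability 2 x Phi(1.598/ratio) - 1, which is 42.8% at ratio 2.83 and 57.6% at ratio 2, against a nominal 89%. No assumed CV enters here.

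**Step 3, one participant.** Take CV 3% (TE = 3.45 mmHg) and an observed fall of 5 mmHg.
- With SD = 3.45/2 = 1.73, the HDI is -5 +/- 2.76, or -7.76 to -2.24. None lies inside +/-2, so the label is responder.
- With SD = 1.414 x 3.45 = 4.88, the HDI is -5 +/- 7.80, or -12.80 to 2.80. The share inside is [Phi(7/4.88) - Phi(3/4.88)]/0.89 = about 22%, which has no class.

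**Step 4, class shares.** The observed change is taken as N(mu, sqrt(2) x TE) and the rule is integrated over it. Responder means under 1% inside the ROPE and a fall; a dash marks figures not needed here.

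| | CV 2% | CV 3% | CV 5% |
|---|---|---|---|
| No true change, responder, SD = TE/2 | 12.4% | 17.1% | 21.6% |
| same, SD = TE/sqrt(2) | 8.4% | 12.1% | 15.7% |
| same, SD = sqrt(2) x TE | 1.6% | 2.7% | 3.8% |
| No true change, 5-99% band, SD = TE/2 | 65.4% | 61.2% | 51.6% |
| same, SD = sqrt(2) x TE | 94.2% | 91.0% | 87.4% |
| True fall 5 mmHg, responder, SD = TE/2 | 64.9% | 53.0% | 43.3% |
| same, SD = TE/sqrt(2) | 56.4% | 44.2% | 34.7% |
| same, SD = sqrt(2) x TE | 27.4% | 18.2% | 12.4% |
| No true change, non-responder, SD = TE/2 | 6.1% | 0 | 0 |
| same, SD = sqrt(2) x TE | 0 | - | 0 |

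Simulation with 1000 draws per person, as the plan specifies, gave 12.0, 16.5 and 20.6% for the first row. With ROPE +/-1.5 to +/-3 mmHg, the no-change responder shares are 7-24% (TE/2), 5-17% (TE/sqrt(2)) and 1-4% (sqrt(2) x TE).

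**Step 5, if TE is a single-reading, within-visit error.** With independent errors the mean of two readings has error TE/sqrt(2), so the change has SD = TE and TE/2 is 2 times too small. But the 4 mmHg rule limits TE. If differences between accepted readings are symmetric, unimodal and within +/-4, their SD is at most 4/sqrt(3) = 2.31, so TE is at most 2.31/sqrt(2) = 1.63 mmHg, or 1.63/115 = 1.42%. At CV 1.0-1.4% the false-responder share is only 0.6-2.4% with TE/2. This takes within-visit error as the only error.

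**Step 6, when non-responder is reachable.** At an observed change of 0, more than 99% inside +/-2 needs an SD of at most about 1.28 mmHg. Under sqrt(2) x TE, that means TE = 1.28/1.414 = 0.91 mmHg, a CV of about 0.8%.

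**The case against.** The strongest objection is that the section never defines its CV or names the BP measure, so no error factor is proven. A reader might infer that the plan certainly understates the SD by 2.83. The documents do not support that. If TE were a single-reading error and eight independent readings were averaged per visit, the change would have SD sqrt(2) x TE/sqrt(8) = TE/2, exactly as printed. The cuff value averages two, but the protocol also records beat-to-beat BP averaged over minutes and 24-hour BP. The size criticism is therefore conditional, and under the within-visit reading its practical effect is small.

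The unmatched bracket also matters. A root sign or an opening bracket may have been lost in extraction. A reader might compute a definite SD by putting a CV into the formula as printed, and derive class shares or conclude that some class can never occur. Those results would rest on damaged text, and the 1000 draws add simulation noise near the cut-offs. What survives every reading is that TE is relative and is never converted to mmHg.

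On direction, the text does speak of hypotensive effects, so the authors probably mean falls. The cut-offs simply do not say so, which is a matter of wording.

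Finally, the corrected rule labels few people. That is true, and it reflects how little one pre-post pair says about one person.

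**Conclusion.** The point holds in conditional form. Two defects can be read directly from the section: no route from TE to mmHg with an undefined CV and BP measure, and no class for 5-99% of the HDI inside the ROPE. That unlabelled band would hold 52-65% of no-change participants under TE/2 on the stated assumptions.

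The third defect depends on what TE is. If it is the mmHg error SD of a visit value, TE/2 is 2.83 times too small (2 times with a lost root sign), whatever the CV. The sizes in mmHg and the class shares do depend on the assumed mean SBP, baseline SD and CV: 12-22% false responders with TE/2, or 8-16% with TE/sqrt(2), against 2-4% with the matching SD.

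A reader might also infer that the trial's main conclusions are at risk. They are not: the analysis is labelled exploratory, and the main outcomes, mixed models and N = 50 do not use this SD. It is worth correcting before anyone is classified.

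**What to change.** Amend the responder section as follows.

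- Name the BP measure and state the source of TE.
- Define TE in mmHg, separately for SBP and DBP, as the between-visit error SD of the visit value analysed (for the cuff, the mean of the last two readings).
- Use SD = sqrt(2) x TE for the change.
- Keep the existing cut-offs and complete them: under 1% responder, 1 to under 5% likely responder, 5-99% undecided, over 99% non-responder.
- Apply both responder classes to falls only and report rises separately.

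The effort is a few lines of SAP text and R code. The SD and the classes should be changed together, because a larger SD moves more people into the middle band. The price is a less decisive rule. On the assumptions above, 87-94% of no-change participants become undecided, and the non-responder class is empty unless the visit-value CV is below about 0.8%. At a true fall of 5 mmHg, the difference in the Sample size section ("detect SBP mean differences of at least 5 mmHg over time and groups"), the responder share drops from 43-65% with TE/2 to 12-27%.
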